### 3.5. Study Endpoints

Definition of the assessment of time-related study efficacy endpoints:

Time-related efficacy study endpoints assessment will start at time 0 defined as the start time of the chemotherapy administration on Day 1 of each of the three cycles.

CINV indicators, such as nausea and vomiting, their intensity and frequency and Quality of Life will be evaluated during the acute phase of emesis, from 0 to 24 hours from the start of chemotherapy, in the delayed phase of emesis, from 24 to 120 hours from the start of chemotherapy, and overall during each day (i.e., day 1, 2, 3, 4 and 5) from the start of chemotherapy.

The primary endpoint will be the proportion of complete responses (no emetic episode and no rescue medication), during the overall phase (0-120h), after the start of the MEC administration over three cycles of chemotherapy.

Clinical secondary endpoints will be evaluated during each cycle:

- Complete response during the acute (0-24h), delayed phase (>24-120h), overall (0-120h) and daily in each cycle;
- No emetic episode during the acute, delayed and overall phase and daily in each cycle;
- Number of vomiting episodes during the acute, delayed and overall phase and daily in each cycle;
- No rescue medication during the acute, delayed and overall phase and daily in each cycle;
- No significant nausea (maximum MAT scale = 2) during the acute, delayed and overall phase and daily in each cycle;
- No nausea (MAT scale = 0) during the acute, delayed and overall phase and daily in each cycle;
- Complete protection (no emetic episode, no rescue medication and no significant nausea) during the acute, delayed and overall phase and daily in each cycle
- Nausea and Vomiting-related quality of life indicators (through the Functional Living Index Emesis scale)
- Collection of chemotherapy delays and/or dose reductions (Delay of chemotherapy administration due to CINV will be also evaluated as part of health economic endpoints, see below)

Health economic endpoints will be evaluated during the study cycles:

- Number of days and daily doses of rescue medication administered for the treatment of CINV
- Number of re-hydration bags given for at least grade 2 vomitings (CTCAE v5)
- The number of days of unplanned hospitalisations related to CINV and department of hospitalization (type of ward)
- The number of outpatient physician visits and health care consultations due to CINV (e.g., general practitioner)
- The number of unplanned laboratory test including those at unplanned hospitalisations due to CINV
- Discontinuation of chemotherapy treatment due to CINV
- Delay of chemotherapy administration due to CINV
- Days of absence from work

CONFIDENTIAL

Confidential	MyRisk	Date: 05 February 2024
	Protocol	
	PROTOCOL NUMBER: IBA1160	Version: 5.1

## 3.6. Study Procedures

### 3.6.1. Calculation of CINV score

Calculation of CINV score will be part of eCRF on factors 1-7 in the above list of predictive factors. Patients with a score of  $\geq 13$  will be the target population. Factor 8 is part of the model calculating CINV risk score, but as it needs to be completed at the day of the chemotherapy administration it creates significant logistical issues with randomisation, antiemetic prescriptions, and patients' waiting and travel arrangements, hence it will not be used to calculate this score in the present study. Adjustment to the risk score to reflect this change has been considered and hence the predictive score for this study is set to  $\geq 13$  instead. This score also maximizes appropriate recruitment and increases the sensitivity of the prediction (true positive rate) to 97.4%. This factor, however, alongside several additional others will be measured and will be used in the refinement of the predictive model at the end of the trial.

### 3.6.2. Data Collection

Data will be collected using the following data collection tools:

#### **MASCC Antiemesis Tool (MAT)**

This is an eight-item scale measuring acute and delayed nausea and vomiting in patients receiving chemotherapy. It has shown high reliability, contrasted groups, and concurrent validity, and moderate to high levels of recall.

#### **Functional Living Index Emesis (FLIE)**

This is an 18-item Likert-type scale measuring the impact of chemotherapy-induced nausea and vomiting on patients' daily function. It is a commonly used scale in antiemetic trials.

#### **Patient's diaries**

Patients will indicate in their diaries the followings from Day 1 to Day 5 of each chemotherapy cycle:

- The intensity of nausea (scale derived from MAT)
- Number of emetic episodes (derived from MAT)
- Rescue medication, either prescribed or non-prescribed
- Adverse events (symptoms of any kind)

#### **Electronic Case Record Form**

Patients will be evaluated for 3 consecutive cycles, whichever the duration of their chemotherapy schedule and number of cycles.

All the data will be collected in an electronic Case Record Form (eCRF) by an attending physician, including the data collected by each patient in a Patient's diary and MAT.

Electronic CRF will contain all the required sociodemographic and clinical data (including information about diagnoses, treatment, rescue medication, medical history, demography, smoking history) divided into particular forms according to the coherence and logical structure to keep a simple and user-friendly data entry system for investigators.

Adverse event data will be collected on a separate form in eCRF and selected data will be automatically reported to the sponsor for pharmacovigilance purposes (see chapter 10). It is at the discretion of the Investigators according to his/her clinical judgment to decide which of the symptoms reported in the patient's diary are to be considered AEs, as defined in the study protocol (see paragraph 10.1) and collected as such in eCRF.

CONFIDENTIAL

Confidential	MyRisk	Date: 05 February 2024
	Protocol	
	PROTOCOL NUMBER: IBA1160	Version: 5.1

The report will be customized for this project and will contain all the required information.

Data will be collected in an electronic database (eCRF), fully customized to the structure and requirements of the project. Records will be stored under a specific identity number (ID) which will not allow any backward identification of any individual patient. The unequivocal identification of patients will be only known to the treating physician or to an authorized healthcare professional or designated personnel under a contract with a site (on-site data monitoring, see chapter 5.0).

Data will be collected in eCRF by the Investigator(s) or trained study member.

Each patient will fill in the FLIE at the end of each cycle and return this to the attending physician (see below). The collected questionnaires will be then periodically sent to the data management CRO for data entry.

Data from the Patient's diary and MAT will be digitalized on-site into the eCRF to become part of the electronic database.

The eCRF screen will be available in English and local languages where required (e.g., Chinese, German).

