### 10.1. Definitions

An AE is any untoward medical occurrence in a patient or clinical investigation subject administered a pharmaceutical product and which does not necessarily have to have a causal relationship with this treatment. An AE can therefore be any unfavorable and unintended sign (including an abnormal laboratory finding), symptom, or disease temporally associated with the use of a medicinal investigational products, whether or not considered related to the medicinal investigational products.

AEs include the following types of occurrences:

- Other medical experiences, regardless of their relationship to the study drug, such as injury, surgery, accidents, increased severity of pre-existing symptoms, apparently unrelated illnesses, and significant abnormalities in clinical laboratory values, physiological testing, or physical examination findings;
- Reactions from drug overdose, abuse, misuse, medication errors, withdrawal, hypersensitivity, or toxicity;
- Clinically relevant abnormal findings, including laboratory abnormalities, as well as worsening of any pre-existing condition at each visit;
- Adverse drug reactions.

Planned surgical interventions or planned hospitalizations scheduled prior to the informed consent but performed during the study (e.g. corrective procedures, biopsy, additional chemotherapy cycles, etc.) should NOT be considered AEs.

An Adverse Drug Reaction (ADR) is any noxious and unintended response associated with the investigational medicinal product at any dose. Response in this context means that a causal relationship between a medicinal product and an AE is at least a reasonable possibility.

CONFIDENTIAL

Confidential	MyRisk	Date: 05 February 2024
	Protocol	
	PROTOCOL NUMBER: IBA1160	Version: 5.1

A Serious Adverse Event (SAE) is any event that suggests a significant hazard, contraindication, side effect, or precaution, whether or not it is considered to be associated with the study drug. A SAE is an AE that meets any of the following criteria:

- Results in death. This includes any death that occurs during the conduct of a clinical study, including deaths that appear to be completely unrelated to the study drug (e.g. car accident);

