### 10.2.1. Severity

The severity of an AE will be rated by the Investigator according to the descriptions and grading scales of the Common Terminology Criteria for Adverse Events (CTCAE) version 5, as follows:

- Grade 1 Mild; asymptomatic or mild symptoms; clinical or diagnostic observations only; intervention not indicated

CONFIDENTIAL

Confidential	MyRisk	Date: 05 February 2024
	Protocol	
	PROTOCOL NUMBER: IBA1160	Version: 5.1

- Grade 2 Moderate; minimal, local or noninvasive intervention indicated; limiting age-appropriate Instrumental Activities of Daily Living (ADL)\*
- Grade 3 Severe or medically significant but not immediately life-threatening; hospitalization or prolongation of hospitalization indicated; disabling; limiting self-care ADL\*\*
- Grade 4 Life-threatening consequences; urgent intervention indicated
- Grade 5 Death related to AE

(\*) Instrumental ADL refers to preparing meals, shopping for groceries or clothes, using the telephone, managing money, etc. (\*\*) Self-care ADL refers to bathing, dressing, and undressing, feeding self, using the toilet, taking medications, and not bedridden.

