### 10.3. Recording of AEs

All AEs (including SAEs) starting from the time of informed consent signature up to the end of the study must be collected in the eCRF, irrespective of relatedness to the study drug.

SAE should be collected and reported within 24 hours.

Any related SAE (based on Investigator judgment) beyond the end of the study may be recorded on the SAE Reporting Form.

SAEs must be followed up by the Investigator until symptom resolution or until the condition stabilizes or the patient is lost to follow-up.

Non-serious AEs must be followed up by the Investigator until the end of the study. At the end of this follow-up period, all unresolved non-serious AEs will be documented on the eCRF as “not recovered”.

Clinically relevant abnormal findings, including laboratory abnormalities, as well as worsening of any pre-existing condition at each visit shall be recorded as an AE.

Any abnormalities seen at baseline should not be recorded as an AE.

The Investigator will be responsible for ensuring that the correct information concerning all AEs is entered on the appropriate eCRF pages and in the SAE Reporting Form as applicable.

CONFIDENTIAL

Confidential	MyRisk	Date: 05 February 2024
	Protocol	
	PROTOCOL NUMBER: IBA1160	Version: 5.1

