### 10.3.1. Reports of Lack of efficacy

Lack of efficacy will be recorded in the eCRF and classified according to its seriousness. Whenever the signs and symptoms considered as lack of efficacy are nausea and vomiting and occurring during the study (up to 5 days after the study drug(s) and dexamethasone administration), these will not be recorded in the AE section of the eCRF, unless it meets the criteria for a SAE or the Investigator considers the episode(s) of nausea and vomiting to be caused by a reason other than lack of efficacy of study treatment.

If at any time during the study, a sign /symptom of lack of efficacy meets a SAE criterion, it is to be reported to the Sponsor and recorded in the AE/SAE section of the eCRF. The report shall clearly state "lack of efficacy" as an SAE.

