**I suffered from adverse event or symptoms of any kind in the 3rd day after chemotherapy.**

Yes  No  (Select one)

If yes, please describe any symptom you suffered from:

.....  
.....  
.....

Please follow described AE and complete SAE/AE form in eCRF based on these data and patient's data you get at visit.

(to be followed by investigator)

CONFIDENTIAL

Confidential	MyRisk	Date: 05 February 2024
	Protocol	
	PROTOCOL NUMBER: IBA1160	Version: 5.1

#### DAY 4

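### Section 3.6.2 leaves the unblinded investigator to judge which diary symptoms become AEs, and no check in the protocol or SAP compares diary symptoms with recorded AEs by arm

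*Protocol*

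**What the plan says.** Protocol section 3.6.2 (Electronic Case Record Form) makes it "at the discretion of the Investigators according to his/her clinical judgment to decide which of the symptoms" from the diary "are to be considered AEs, as defined in the study protocol (see paragraph 10.1) and collected as such in eCRF". The diary itself collects symptoms of any kind on Days 1 to 5 of each cycle (section 3.6.2, Patient's diaries).

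Section 10.1 is broad: "An AE is any untoward medical occurrence in a patient or clinical investigation subject administered a pharmaceutical product", and "An AE can therefore be any unfavorable and unintended sign (including an abnormal laboratory finding), symptom, or disease temporally associated" with use of the product, related or not. Section 10.2.1 has a lowest grade of "Grade 1 Mild; asymptomatic or mild symptoms; clinical or diagnostic observations only; intervention not indicated", so there is no severity threshold.

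Section 10.3 states that "All AEs (including SAEs) starting from the time of informed consent signature up to the end of the study must be collected in the eCRF", whatever the causality; the opening of section 10 says the same. Two written exclusions apply to symptoms: abnormalities seen at baseline (10.3), and nausea and vomiting regarded as lack of efficacy (10.3.1), unless serious or attributed to another cause.

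The symptom item on the diary pages in Appendix 2 (Days 3 and 4 are shown) tells the investigator: "Please follow described AE and complete SAE/AE form in eCRF based on these data". It does not mention discretion.

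The study is open label (section 3.1). SAP section 9.1 presents all tables by treatment group, and SAP section 9.5.1 plans no formal safety tests.

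**The concern.** A site that follows the diary page enters the symptom. A site that relies on 3.6.2 may decide that it is not an AE. Both can claim to follow the protocol, and no criteria or recorded reason separate the two decisions. The person deciding knows the arm.

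Safety is a secondary objective, and with no formal tests the reader relies on the raw percentages by arm. If entry of diary symptoms differs between arms, those percentages mix drug effect with recording habit, and the reported outputs would not show it.

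**Working it through.** The plan states no figure on this point, so there is none to reproduce. The check is a comparison of texts, followed by a simple illustration.

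**Step 1: what is left to decide.** Section 10.1 sets no causality threshold, and 10.2.1 grades mild symptoms. A diary symptom that is new or worse after dosing will therefore normally meet the definition. What remains is to apply the baseline exclusion (10.3) and the lack-of-efficacy exclusion (10.3.1). Section 3.6.2 does not confine the judgment to these two, gives no further criteria and asks for no reason.

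**Step 2: would a planned check show differential entry?**

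| Planned activity | What it compares |
|---|---|
| Reconciliation before lock (SAP 3 and 9.5.1) | SAEs in the database with SAEs reported to the sponsor |
| Diary quality control (Protocol 7, Quality Control Process) | Paper diary with the digitised copy |
| Data review (Protocol 7 and 7.1) | Medical review of AEs, outliers and systematic errors; no diary-to-AE comparison named |
| Discrepancy checks on digitised data (SAP 3 and 9.1.4) | Digitisation and consistency errors; comparison with AE forms not named |
| Safety tables 14.3-1 to 14.3-3 and the AE listings (SAP 10) | Exposure and recorded AEs only |

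None is specified as diary symptoms against AE entries, by arm or overall. Source checking is unclear too: section 7.1 says source documents will not be monitored, while section 5 lists on-site monitoring. The Data Validation Plan is a separate document and could contain such a check; the protocol and SAP do not say so.

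**Step 3: how unequal entry would act.** Recorded rate = symptom rate × probability of entry. With the same symptom rate r in both arms and entry probabilities a and b, the difference is r × (a − b) and the ratio is b / a. All inputs below are assumptions.

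| r | a | b | Recorded rates | Difference | Ratio |
|---|---|---|---|---|---|
| 20% | 90% | 90% | 18% and 18% | 0 points | 1.00 |
| 20% | 90% | 80% | 18% and 16% | 2 points | 0.89 |
| 40% | 90% | 80% | 36% and 32% | 4 points | 0.89 |
| 20% | 90% | 70% | 18% and 14% | 4 points | 0.78 |
| 40% | 90% | 70% | 36% and 28% | 8 points | 0.78 |

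Incomplete entry that is equal in both arms lowers both rates but leaves the ratio at 1.00. Only a difference in entry between arms distorts the ratio.

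**Step 4: the 10.3.1 window.** The lack-of-efficacy exclusion runs "up to 5 days after the study drug(s) and dexamethasone administration". Sections 1 and 3.4 give dexamethasone on Day 1 and let it be considered on Days 2 and 3 for some regimens. Counted from Day 1, five days is close to the Day 1 to 5 diary and MAT period. Counted from a Day 3 dose it reaches Day 3 + 5 = Day 8. The text does not say which dose starts the window.

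**The case against.** Quoted without its ending, the 3.6.2 sentence might lead a reader to infer that it overrides the AE definition. It does not: it asks whether a symptom meets 10.1. The collect-all rule covers events that are AEs, and 10.3 and 10.3.1 require someone to set some diary symptoms aside. That objection stands, and it reduces the fault to loose wording in tension with 10, 10.3 and the diary page.

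The possible impact can also be called speculative. Nothing in the documents suggests that entry differs by arm, and safety is descriptive. Section 2.1 attributes the known drug-related effects, headache and constipation, to the drug classes, and both arms receive a 5-HT3 antagonist. Unentered symptoms stay in the diary record, and quarterly data review looks for systematic reporting errors. All of this is fair, and it is why the size must be given as unknown. It does not supply the missing comparison: a record that is kept but never compared with the AE forms reveals nothing.

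Finally, rewording cannot make the safety assessment blind. Patients know their arm when they fill in the diary, and severity and relatedness remain with the same investigator. That also stands. The gain is that the entry step becomes uniform and visible.

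**Conclusion.** The point holds as a gap in wording and checking. Discretion without criteria or a recorded reason sits beside a broad definition, a collect-all rule and a contrary diary instruction, in an open-label trial with AE tables by arm. Differential entry is possible and would not be seen in the planned outputs. Its size is unknown; the 2 to 8 points shown rest wholly on assumed rates. The primary endpoint, built from emesis and rescue medication, does not depend on the AE form.

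A reader might also infer that AEs will be filtered by arm. The documents describe no such procedure; this is only a risk.

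A reader might further infer from the 10.3.1 window that nausea and vomiting on Days 6 to 8 reach no dataset. The documents do not support that. Section 10.3.1 says lack of efficacy is recorded in the eCRF and excludes it only from the AE section. Visits 2 to 4 collect safety findings by inquiry as well as from diaries. Day 8 arises only if an optional Day 3 dose starts the window. What remains is an ambiguous starting point.

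**What to change.** 1. **Protocol 3.6.2 and Appendix 2.** State that every diary symptom meeting 10.1 is entered as an AE unless excluded by 10.3 (seen at baseline) or 10.3.1 (nausea or vomiting as lack of efficacy). Require a short coded reason for each symptom not entered. Give the same rule in the diary instruction.
2. **Data review and SAP 9.5.1 and 10.1.** Add a recurring check by arm and one safety table: patients per cycle with a diary-reported symptom, with an AE starting on Days 1 to 5, with both, and with a symptom but no AE, by reason. SAP 7.1 already places diary data in the clinical database. This assumes that the symptom item is among the digitised fields, which the documents do not list one by one.
3. **Minor: Protocol 10.3.1.** Reconcile the window wording with the Day 1 to 5 diary and MAT period, so that the starting point is explicit.

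The cost is a protocol and SAP wording change, some extra entry at sites and one more table. AE counts may rise in both arms. Patients' knowledge of their own arm remains, so the by-arm safety comparison should still be read as open label.

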### 3.6.3. Study visits procedure

No study-specific activities will be completed before signed informed consent form is obtained from patients. Study procedure covers five patient's visits at the site.

#### Visit 0

Visit 0 is a screening visit conducted within 2 weeks before chemotherapy administration on cycle 1 or alternatively on Day 1 of chemotherapy Cycle 1. The case of Visit 0 and 1 are combined the patient will still be given adequate time for consideration and consent before the study enrolment.

Investigator considers whether the selected patient meets the predefined eligibility criteria. All predictive individual factors as reported earlier will be collected in eCRF. The risk score will be calculated automatically based on predictive factors No. 1 – 7 (see 3.3.3. Risk Factors for CINV). These parameters will be used to identify the patients with a CINV risk score  $\geq 13$  (see 3.3.1. Inclusion Criteria). If the patient complies with all the inclusion and exclusion criteria and signs informed consent, he/she is enrolled in the study. If the patient is WOCBP a pregnancy test is done to confirm eligibility. Data from screening visit will be collected in appropriate forms in eCRF.

The randomization procedure can be conducted either during Visit 0, Visit 1 or any time between Visit 0 and Visit 1. The patient is randomized by using an algorithm in eCRF into one of the intervention groups (see sections 3.4. Intervention and antiemetic treatment and 3.4.2. Randomization procedure). If randomization occurs any time before visit 1, it is required to check during Visit 1 that the patient receives the correct treatment assigned according to the intervention groups. The drugs must be correctly stored between the randomization and drug administration at Visit 1.

#### Visit 1

Visit 1 is a visit on Day 1 of chemotherapy Cycle 1.

WOCBP are tested for pregnancy by a urine dipstick prior to dosing the antiemetic treatment.

The patient is asked about the additional predictive factors (anxiety in the previous 24 hours &  $<7$ h of sleep the night before chemotherapy).

The patient is assigned to the treatment and randomized by using an algorithm in eCRF into one of the intervention groups (see sections 3.4. Intervention and antiemetic treatment and 3.4.2. Randomization procedure).

The patient receives antiemetic and chemotherapy at a due time after antiemetic is given.

Data of cycle 1 is collected in eCRF in an appropriate form.

Before the patient leaves the site, he/she receives FLIE, MAT, and a Patient's diary to answer questions regarding the severity of nausea and vomiting, rescue medication, adverse events. The patient will be instructed by the doctor how to fill in and asked to bring it back at visit 2.

CONFIDENTIAL

Confidential	MyRisk	Date: 05 February 2024
	Protocol	
	PROTOCOL NUMBER: IBA1160	Version: 5.1

## Visit 2

Visit 2 is a visit on Day 1 of chemotherapy Cycle 2.

The patient's diary, MAT, and FLIE are collected and checked by the investigator. In the case of missing answers, the investigator will need to complete them with the patient. The patient's eligibility for the chemotherapy is confirmed by checking changes of the screening visit parameters for the algorithm re-calculation. This re-calculation is collected in eCRF. This re-calculation has no impact on patient participation in the study and the randomized group.

Female patients of childbearing potential are tested for pregnancy by a urine dipstick prior to dosing the antiemetic treatment.

The patient receives antiemetic and chemotherapy at a due time after antiemetic is given.

Data of cycle 2 is collected in eCRF in appropriate forms.

Before the patient leaves the centre, he/she receives FLIE, MAT, and a Patient's diary to answer questions regarding the severity of nausea and vomiting, rescue medication, adverse events. The patient will be instructed by the doctor how to fill in and asked to bring it back at visit 3.

## Visit 3

Visit 3 is a visit on Day 1 of chemotherapy Cycle 3. The procedure is the same as described for Visit 2.

The patient's diary, MAT, and FLIE are collected and checked by the investigator. In the case of missing answers, the investigator will need to complete them with the patient. The patient's eligibility for the chemotherapy is confirmed by checking changes of the screening visit parameters for the algorithm re-calculation. This re-calculation is collected in eCRF. This re-calculation has no impact on patient participation in the study and the randomized group.

Female patients of childbearing potential are tested for pregnancy by a urine dipstick prior to dosing the antiemetic treatment.

The patient receives antiemetic and chemotherapy at a due time after antiemetic is given.

Data of cycle 3 is collected in eCRF in appropriate forms.

Before the patient leaves the centre, he/she receives FLIE, MAT, and a Patient's diary to answer questions regarding the severity of nausea and vomiting, rescue medication, adverse events. The patient will be instructed by the doctor how to fill in and asked to bring it back at visit 4.

## Visit 4

Visit 4 is a visit on Day 5 of Cycle 3 or before the start of the next programmed chemotherapy cycle.

It is the final visit of the study. FLIE, MAT, and Patient's diary are collected and recorded information checked. All patient's data in eCRF are collected, checked, and validated.

Besides predictive risk factors to calculate the Risk scoring algorithm, further additional factors will be collected and evaluated to confirm the risk scoring algorithm.

Each visit procedure in detail is described in the following chapters. The Study Flow Chart is reported in Appendix 1.

### 3.6.3.1 BASELINE/SCREENING: VISIT 0

